1.0 Objectives / Specific Aims

Fenofibrate, a safe and long-established lipid-lowering agent, was recently discovered to have unexpected yet dramatic therapeutic effects on diabetic retinopathy (DR) in two large clinical trials (1,2). Intriguingly, the retinal benefits were independent of plasma lipids, suggesting novel mechanisms of action. Furthermore, evidence indicates that fenofibrate's beneficial effects extend to many other microvascular complications of diabetes.

Our aims are: 1) to recruit a cohort of 40 well-characterized fenofibrate-naïve patients with type 2 diabetes who will receive oral fenofibrate 160 mg/day for six weeks; this work will establish a clinical sample repository, collected immediately prior to and after treatment, to enable us to 2) characterize the global plasma proteome before and after fenofibrate treatment and future follow-up studies. We expect to gain novel insights into the systemic effects of fenofibrate on the pathophysiologic processes that drive diabetic vascular complications. This will generate new hypotheses about the common root causes of diabetic complications and complement data being accrued in ongoing studies of retinopathy, nephropathy, atherosclerosis, and complications of pregnancy that integrate human data with and animal/cellular model systems. The ultimate translational impact of the work will be the development of proactive means to block a range of complications early in their evolution, either through the development of more selective targeted therapies, and/or finding new disease indications for existing drugs.

To translate this into new preventive and/or therapeutic measures, we hypothesize: 1) that fenofibrate has mechanisms of action beyond PPAR α agonism that attenuate microvascular complications of diabetes; and 2) that observable treatment-induced changes in the constituents of plasma will reflect the underlying effects of the drug on target tissues.

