upregulating hepatic LDL receptors. It is also unclear whether the benefits of fenofibrate are mediated via PPAR α or some novel mechanisms of action (8-13). In fact, recent data from our group using a human retinal pigment epithelial (RPE) barrier model showed that fenofibrate, but not other PPAR α agonists (WY14643, gemfibrozil, bezafibrate), attenuated the toxic effects of oxidized LDL on barrier integrity (14). Thus, fenofibrate may or may not be the answer, but it certainly provides important clues, and our lack of understanding of its systemic effects on the diabetic milieu is a barrier to the development of new treatments. Discovery of the mechanisms and pathways of action could yield a new generation of drugs that can protect multiple tissues from the effects of diabetes, blocking disease development proactively instead of reacting to end-stage complications.

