5.0 Inclusion and Exclusion Criteria/ Study Population

Type 2 diabetes is highly prevalent in our endocrine clinic population and recruitment of sufficient numbers of volunteer subjects should be easily achieved. We anticipate recruitment of subjects to occur over six months, such that all study samples will be available for LC-MS/MS analysis within eight months of start-up. We have a long track record of collaboration with the SCTR NEXUS facility, e.g. through DCCT/EDIC, and are familiar with their policies and procedures. While our sample size is adequate for discovery research related to the systemic effects of fenofibrate treatment, any human study of outcomes would require a much larger cohort and longer period of follow-up. All subjects will be screened by their provider to ensure the eligibility for the study according to the criteria outlined below.

Inclusion criteria:

- Male or female aged ≥ 18 and ≤ 70 years

- Type 2 diabetes of at least one year's duration; stable glycemic control (no more than 1.0% change in HbA1c in the previous six months, but no limit on HbA1c)
- Triglycerides >150 mg/dL (in the previous six months)

Exclusion criteria:

- Previous use of Fenofibrate or other fibrates
- Pregnancy/lactation
- Active malignancy
- Recent cardiac event or congestive heart failure
- Active liver disease (LFT's > 2x's normal value)
- Significant renal impairment (serum creatinine > 2mg/dl)
- Current warfarin use

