- Participants will be scheduled for visit 2 in six weeks.

Visit 2:

- Upon arrival at the SCTR NEXUS clinic, a physical examination will be performed by either the PI or co-investigators. Clinical data will be recorded to include demographic information, and medications, and anthropometric information.
- Fasting blood (80ml) will be obtained for follow-up labs (BUN, Cr, urine microalbumin, LFTs, CPK, Lipid Profile, HbA1c, TSH, C-peptide) and processed to yield heparin,

EDTA, and citrate-plasma, serum, and pellets (sufficient for all planned analyses). A timed morning urine sample will be collected with the volume recorded. Samples will be stored in ultra-low freezers for proteomics and subsequent confirmatory assays (by ELISA).

- Participants will then undergo an assessment of adverse events and study drug compliance, which will be determined by pill count.
- Following venipuncture, participants will be given a choice of breakfast foods from which to choose by the IRB approved personnel and a place to eat.
- Participants will receive a gift card at the completion of visit two in the amount of \$25.
- The plasma proteomic signature will be generated by LC-MS/MS (n=80 proteomes) of each subject before and after fenofibrate treatment. Bioinformatic approaches will then be employed based on geneset enrichment analysis to identify the biological processes/signaling networks impacted by treatment.

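### Does describing the proteomic analysis as finding networks affected by treatment claim more than a single-arm before/after study can show?

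*Protocol*

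**What the plan says.** Section 1.0 gives two aims: to recruit 40 fenofibrate-naïve patients with type 2 diabetes, treat them for six weeks and bank samples from before and after; and to "characterize the global plasma proteome before and after fenofibrate treatment". The expected product is stated there too: "This will generate new hypotheses about the common root causes of diabetic complications".

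A separate closing paragraph of Section 1.0 sets out two hypotheses. The first is "that fenofibrate has mechanisms of action beyond PPAR α agonism that attenuate microvascular complications of diabetes"; the second is "that observable treatment-induced changes in the constituents of plasma will reflect the underlying effects of the drug on target tissues".

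Section 10.0 describes the analysis: "The plasma proteomic signature will be generated by LC-MS/MS (n=80 proteomes) of each subject before and after fenofibrate treatment". Gene-set enrichment is then applied "to identify the biological processes/signaling networks impacted by treatment".

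Section 4.0 says that no specific endpoints have been fixed. Section 5.0 calls the sample size adequate for discovery and adds that "any human study of outcomes would require a much larger cohort and longer period of follow-up". Section 16.0 says there is no evidence of benefit from use as short as this.

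**The concern.** The stated purpose of the enrichment step is causal, whereas the second aim is descriptive. In this design, visit and assigned drug coincide in every sample. A protein that moves between the visits may have moved because of fenofibrate, or because of diet, season, trial participation, a change in other medication, or sample handling and assay run. Enrichment works on the same difference, so it inherits the ambiguity. None of the protocol's disclaimers addresses this point: Section 5.0 limits inference about clinical outcomes and Section 16.0 limits expected benefit, but neither says that a before/after change need not be a drug effect.

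The hypotheses in Section 1.0 add to the impression of overreach. The first concerns routes other than PPAR α and attenuation of complications. The protocol's own evidence on such routes comes from a cell model with comparator agonists, in which "fenofibrate, but not other PPAR α agonists (WY14643, gemfibrozil, bezafibrate), attenuated the toxic effects of oxidized LDL on barrier integrity" (Section 2.0). This study has no comparator agonist. The second hypothesis links plasma to target tissue, and only blood and urine are collected. If the results were reported as established drug effects, follow-up work could be built on changes that fenofibrate did not cause.

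**Working it through.** **1. The plan's own figure.** Inputs: 40 participants (Sections 1.0 and 6.0) and two sampling visits (Section 10.0). 40 × 2 = 80 proteomes, as stated.

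**2. What the contrast can separate.** A within-person model has 40 participant intercepts plus one visit term: 41 columns, rank 41. Adding a term for assigned drug gives 42 columns, still rank 41, because the drug column equals the visit column. Splitting the drug term into PPAR α and other routes gives 43 columns, still rank 41. This is simply another way of saying single arm. It applies to assigned treatment. Actual exposure can vary through early stopping (Section 14.0) and compliance (pill count, Section 10.0), but that variation is not randomised and does not repair the confounding.

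**3. What a visit effect could do.** The protocol gives no alpha, effect size or standard deviation, so this step is an illustration on assumed values. Take a two-sided paired t-test at 0.05, n = 40, with no drug effect and a shift between visits of d standard deviations of the within-person change. The noncentrality is d × √40; at d = 0.3 it is 0.3 × 6.325 = 1.90.

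| Assumed d | Chance of nominal significance per protein |
|---|---|
| 0 | 5% |
| 0.1 | 9.5% |
| 0.2 | 23.5% |
| 0.3 | 45.7% |
| 0.4 | 69.4% |
| 0.5 | 86.9% |

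In a simulated comparison of 20 against 20 with the same shift in both groups (d = 0.2, 0.3 and 0.5), the rate stays at 5.0% to 5.1%. The mechanism is real. Nothing in the protocol indicates which d, if any, applies.

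**4. What a change of wording would alter.** Suppose Section 10.0 spoke of networks that differ between the two visits. Participants: 40 before, 40 after. Proteomes: 80 and 80. The contrast, the enrichment method and every value in step 3 stay the same. The same attribution would also still stand in Section 1.0, which calls plasma changes treatment-induced and expects insight into the drug's systemic effects, and in Section 5.0, which describes the discovery work in similar terms.

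**5. The hypotheses.** Section 1.0 places them after the two numbered aims and introduces them as a step towards new preventive or therapeutic measures. No section assigns either one a test, and Section 4.0 fixes no endpoint. They read as the rationale for the programme.

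**6. A possible extra analysis.** One could repeat the comparison without participants whose glucose- or lipid-lowering medication changed between visits. With half-width t(0.975, n−1)/√n in standard deviations of the change, n = 40 gives 0.320, n = 36 gives 0.338 and n = 32 gives 0.361 (assuming 4 or 8 such participants; the protocol gives no number). Such a rerun selects on an event after baseline and does not touch time, diet or participation effects. It is a choice for the analysis plan, which is not at hand.

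**The case for a change.** The strongest case for a change is that the protocol makes two claims of different strength for one analysis and the data support only the weaker. The limit comes from the design, so no analysis plan can remove it without outside assumptions. The causal phrasing is no isolated slip, since Sections 1.0 and 5.0 use similar language. Background drugs and diet are not required to stay constant between visits. The drug's known lipid effects (Section 5.0 aside, Section 3.0 cites a triglyceride reduction of 30-50%) are little help, because the stated interest is in mechanisms independent of lipids, where prior knowledge is thinnest. And the remedy would cost one phrase.

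Most of this stands as a description of the design. It does not show a fault that a changed plan would cure. The phrase is a statement of purpose in exploratory work, and the possible harm lies in how a later report is worded. The protocol also supplies material for a sensible reading: stable glycaemic control in the six months before entry, fasting samples at both visits, lipids, HbA1c, body measurements and medications recorded at both visits, and a pill count at the second. These allow partial checks and do not replace a control. It would also go too far to say that rival causes are as likely as the drug to explain a change; the documents give no basis for weighing them.

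**Conclusion.** No change to the plan is needed. The before/after contrast alone cannot attribute a difference to fenofibrate, and the purpose clause in Section 10.0 is worded more strongly than that. But a single arm is a fair trade-off for a small discovery study whose declared product is new hypotheses, and rewording the clause would alter no number, analysis, bias or result. The two hypotheses are not presented as tested here, so they contain no error. The size of any visit effect is unknown; the 9.5% to 86.9% range rests on assumed shifts of 0.1 to 0.5 standard deviations and a nominal 0.05 level. The conclusion assumes that the networks found are reported as candidate treatment effects pending controlled follow-up, which is how analysts would ordinarily present uncontrolled discovery data.

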11.0 Collection and Banking (if applicable)

For this work, fasting blood samples (80 ml) will be collected at each of two visits, and processed via centrifugation to yield heparin, EDTA, and citrate-plasma, serum, and pellets (sufficient for all planned analyses). A timed morning urine sample will be collected with the volume recorded. Samples will be alphanumerically coded and correlated to the stored samples. Codes have no association to the participant's identity. Samples will be stored in ultra-low freezers for proteomics and subsequent confirmatory assays (by ELISA). Links to participant identity (including demographic and clinical information) will be accessible to the PI and research coordinator only and links will be destroyed at the study's conclusion. Consent forms and any associated hard documents will be kept in a locked cabinet, in the locked office of the PI.

Specimen/Banking for Future Use

The samples will be stored in ultra-low freezers maintained by the [name] lab on the 9th floor of the Clinical Science Building (CSB). The freezers are housed in room 912, which remains locked and accessible only to members of the [name] lab. Samples will be alphanumerically coded and linked to clinically pertinent information. The samples will be stored indefinitely or until completely used.

Future research may be conducted by [name] or by other researchers who obtain IRB approval for their research. There is potential in the future for genetic analyses of samples and therefore the option to opt out will be made available to participants in the informed consent form.

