12.0 Data Management

Participants' privacy will be protected via alpha-numeric coding of the data once obtained. Names of participants will not be entered in the database, instead they will be identified by assigned code. Information linking the code to the participant will be kept securely by the PI. There will be no link to the participant after study completion. The consent forms, which are the possible way to breach confidentiality, will be stored in the PI's office as well in a secure location. All clinical data pertaining to the study will be stored online in REDCap.

13.0 Provisions to Monitor the Data to Ensure the Safety of Subjects (if applicable)

Adverse event (AE) reporting Adverse events anticipated in this study that involves a fasting blood draw and potential side effects of fenofibrate (for example myalgias, elevation of liver enzymes) are few. Risks associated with drawing blood from the arm include momentary discomfort and/or bruising. Infection, excess bleeding, clotting, or fainting is possible, although unlikely.

Risk minimization These risks will be minimized by allowing only well-trained clinical research staff of the SCTR NEXUS facility to perform study procedures and testing according to standard practice, and by making sure study participants clearly understand study procedures before and during the study protocol.

The blood draw will be performed with the subject resting and recumbent. Adequate rest time will be provided after the blood draw to avoid a hypotensive response. Breakfast will be provided at the end of blood draw. Participants will be instructed to report any concerning symptoms. If necessary, adverse events will be reported to the PI and the IRB. Unanticipated non-serious adverse events must be reported from the investigator to the IRB no later than 10 working days after the event or notification to the investigator that the event has occurred, and serious adverse events will be reported within 24 per MUSC IRB guidelines. In absence of moderate or serious adverse events, reports of study progress will be submitted to the IRB for review on an annual basis.

The potential benefits of the research, which may include lowering of cholesterol and the identification of major new risk factors for complications of diabetes, are considered to outweigh the minimal risks involved.

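### Does destroying the identity links at study end strip the banked samples of their clinical data?

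*Protocol*

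**What the plan says.** Three places in the protocol bear on this.

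- **Section 11.0, opening paragraph.** Samples carry an alphanumeric code that has no association with the person's identity. Then: "Links to participant identity (including demographic and clinical information) will be accessible to the PI and research coordinator only and links will be destroyed". The timing follows in the same sentence: "links will be destroyed at the study's conclusion".
- **Section 11.0, banking for future use.** "Samples will be alphanumerically coded and linked to clinically pertinent information. The samples will be stored indefinitely or until completely used". The section also foresees use by other researchers with IRB approval, and offers a genetic opt-out on the consent form.
- **Section 12.0.** Names are not entered in the database; participants appear there under an assigned code. "Information linking the code to the participant will be kept securely by the PI". No link to the participant is to remain once the study is complete. "All clinical data pertaining to the study will be stored online in REDCap".

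The purpose of the repository is given in section 1.0: to enable the investigators to "characterize the global plasma proteome before and after fenofibrate treatment and future follow-up studies".

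**The concern.** The bracket in the destruction sentence names demographic and clinical information next to the links to identity. A reader who takes it as a list of what is destroyed concludes that the tie between sample and clinical record goes at study end. A few lines later the samples are to be kept indefinitely, under a future-use heading, and are described as linked to clinical information. Both cannot hold after the study closes. The same sentence confines access to two roles, whereas the banking paragraph expects other researchers to use the material.

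The stake would be the later use of the bank. A before-and-after plasma sample without sex, age, complication status, medication or laboratory values is of much less use for follow-up work. Destruction cannot be undone, so an error here could not be repaired afterwards.

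**Working it through.** The protocol gives no figure to reproduce, and no error rate, power or sample size depends on the point. The check is a comparison of the text, followed by a count of what each reading would affect.

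**Step 1: what is destroyed.** The grammatical object in section 11.0 is links, and they are links to identity. The bracket can be read in two ways:

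- (a) It describes what the identity links connect a person to, namely that person's demographic and clinical record.
- (b) It adds the clinical information itself, or its tie to the sample, to the items destroyed.

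Under (a), cutting the link removes the route from a name to a record. The record and the code that joins it to a sample both survive.

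**Step 2: test each reading against the rest of the text.**

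| Statement | Reading (a): identity key only | Reading (b): clinical tie also destroyed |
|---|---|---|
| 11.0: codes have no association with identity | Consistent | Consistent |
| 11.0: banked samples are coded, tied to clinical information and kept indefinitely | Consistent | Conflicts |
| 11.0: other researchers may use the bank with IRB approval | Consistent; they would work from coded data, and the two-role limit protects the key | Samples usable, but without annotation |
| 12.0: the link is what joins code to participant | Consistent; same object | Broader than section 12.0 describes |
| 12.0: no link to the participant after completion | Consistent; same event | Goes beyond it |
| 12.0: clinical data held in REDCap under code | Consistent | Would need a deletion step that is stated nowhere |
| 1.0: repository to support future studies | Consistent | Works against it |

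Reading (a) fits every statement. Reading (b) conflicts with the next paragraph of its own section and needs an action that the protocol does not describe.

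**Step 3: count what is affected.**

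- Planned collections: 40 participants (section 6.0) x 2 visits (section 10.0) = 80.
- Reading (a): 0 of 80 lose clinical annotation.
- Reading (b): at most 80 of 80, and only after the study ends. This is a ceiling, because it assumes full enrolment and no withdrawals.
- A count of tubes adds nothing. One of each of the five blood fractions per collection gives 80 x 5 = 400. Withdrawals would lower that figure, and so would material used up in assays, which section 11.0 allows for.

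**Step 4: effect on the study's own analysis.** Section 10.0 states: "The plasma proteomic signature will be generated by LC-MS/MS (n=80 proteomes) of each subject before and after fenofibrate treatment". Section 5.0 expects all samples to be available for that work within eight months of start-up. Pairing a participant's two proteomes needs the participant code and the visit, not the name. Destruction comes at the conclusion of the study, after this work. Proteomes affected: 0 of 80 under either reading.

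**The case for a change.** The best argument for a change is that section 12.0 helps without settling the matter. It never says outright that coded clinical data stay joined to the banked samples once the study is over. Staff managing the bank would turn first to section 11.0, where the bracket sits. The step is irreversible, rewording one sentence is cheap, and a correction is only useful beforehand. A related worry is the genetic opt-out: if it were recorded only on a named consent form, it could not be traced to a sample once the key had gone.

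Part of this stands. The bracket is badly placed, and that the clinical tie outlasts the study is inferred from indefinite storage for future use, not stated. The inference is strong, though. For harm to follow, staff would have to set aside both the next paragraph and section 12.0, and then strip data that no instruction tells them to remove. Irreversibility carries weight only if that chain of events is realistic.

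The opt-out is a matter of record-keeping detail that a repository would ordinarily handle in its procedures. It does not follow from the wording at issue, and the consent pages are not available to check. Simply deleting the bracket would not be free of cost either, since those are the only words in that sentence that extend the two-role access limit to demographic and clinical information.

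**Conclusion.** The concern identifies a real looseness of wording but not a fault in the plan. Sections 11.0 and 12.0 agree if the links destroyed are the key between code and participant, and that is the only reading that fits all the relevant statements. On it, 0 of 80 collections lose their clinical annotation. The contrary reading gives a ceiling of 80 of 80 after study end, but requires acting against two other parts of the protocol.

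No endpoint, sample size, analysis, safety step or within-study result changes either way. The conclusion rests on two assumptions: that the links in section 11.0 are the same object as the link described in section 12.0, and that the REDCap data are kept under code, as section 12.0 indicates. If the sponsor edits the document for other reasons, it could confirm that intent and align the access limit with the banking paragraph and the consent wording. That would be an editorial clarification, and no change to the plan follows from it.
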